Aim 3: Compare the surgical time to complete one sinus side during functional endoscopic sinus surgery after the preoperative use of 0.05% Oxymetazoline or Epinephrine

Hypothesis: There will be no difference in surgical time

Study Design

The study will be a single center prospective randomized double blinded pilot study to compare blood loss and visualization of the surgical field following the preoperative use of pledgets soaked in Oxymetazoline or Epinephrine.

The inclusion criteria will be patients undergoing bilateral endoscopic sinus surgery (ESS) in which the same sinuses and procedures on both sides are the same for CRS with or without nasal polyposis. Exclusion criteria will be pregnancy, known coagulopathy, an international normalized ratio greater than 1.3, a partial thromboplastin time greater than 50 seconds, use of non-steroidal anti-inflammatory drugs in the last 10 days (2 or more doses), use of any antiplatelet agents (eg, warfarin, clopidogrel, berlinta) poorly controlled hypertension with a

preoperative systolic blood pressure of 160mm Hg or greater or a diastolic blood pressure of 90mm Hg or greater, or having any adverse reaction to topical epinephrine or oxymetazoline.

The study will be a paired design study with one nasal cavity receiving epinephrine and the other receiving oxymetazoline. The 1:1000 epinephrine and oxymetazoline solutions both comes in a 30cc vial and each pledget will be wrung out in a similar fashion to keep volume administered similar. The side each drug will be placed on will be randomized using a block randomization scheme on the day of surgery with a block size of four. Two pledgets with the associated medication will be placed into the nasal cavity; one along the floor of the nose and another directed towards the middle meatus.

As a part of routine preoperative workup all patients receive preoperative computed tomography scans of the paranasal sinuses with a navigation protocol. These scans will be assessed using the Lund-Mackay staging system, a standardized radiological grading system used to evaluate CT scans of chronic rhinosinusitis patients. The sinonasal mucosa will also be scored by the surgeon on the day of surgery using a mucosal grading system we have used previously which was modified from a mucosal grading system originally used for grading patients with allergic fungal rhinosinusitis.²

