The patients will be recruited from the practices of 3 fellowship trained rhinologists within our institution.

All data will be deidentified and assigned a random number. Data will be stored on a password protected file on a password protected computer.

Our primary endpoint will be to compare surgical field visualization after the use of epinephrine or Oxymetazoline using the Boezaart grading scale, an inexpensive standardized rating scale used to analyze surgical field visualization during sinus surgery. The operative field will be rated at the conclusion of the procedure by the surgeon. A representative 1 minute video will also be selected for each side. These videos will be blindly reviewed and rated by all 3 surgeons using the Boezaart scale.

Our secondary endpoint will be to compare the amount of blood loss use after the use of epinephrine or Oxymetazoline. This will be done by subtracting the amount of irrigation used from the volume collected in the suction canisters to estimate blood loss. The Neptune 2 Waste Management System (NWMS, Stryker, Kalamazoo, Michigan), a closed suction system that digitally measures the amount of fluid suctioned will be used for more accurate measuring of fluid suctioned.

Both Oxymetazoline and Epinephrine soaked pledgets are routinely used preoperatively before sinus surgery both within our institution and nationally. The choice of which is based on surgeon preference. Both have well established safety profiles. (Higgins, Korkmaz, Orlandi)

Study Population

The inclusion criteria will be patients undergoing endoscopic sinus surgery (ESS) for CRS with or without nasal polyposis. Exclusion criteria will be pregnancy, known coagulopathy, an international normalized ratio greater than 1.3, a partial thromboplastin time greater than 50 seconds, use of non-steroidal anti-inflammatory drugs in the last 10 days (2 or more doses), poorly controlled hypertension with a preoperative systolic blood pressure of 160mm Hg or greater or a diastolic blood pressure of 90mm Hg or greater, or having any adverse reaction to topical epinephrine or oxymetazoline.

The patients will be recruited from the practices of 3 fellowship trained rhinologists within our institution.

Study Procedures

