No adverse events are anticipated. The study should provide no additional risk to the patient.

Any potential adverse events or unanticipated problems will be monitored by the research team and reported as discovered. The research team has a pre-scheduled monthly meetings where this study will be discussed.

Statistics

Statistical significance will be defined as less than 0.05. For quantitative data a 2-tailed paired t-test will be used. Categorical data will be compared using the McNemar's test. For non normally distributed data a Wilcoxon rank-sum test will be used. All patients who are administered both randomized preoperative topical vasoconstrictors will be included in the study.

The blood loss of 355 ± 393 mL seen in sevoflurane group from a previous study we performed in which we used oxymetazoline was used to calculate sample size.² With a proposed difference of 150ml of blood loss with a targeted power of 0.8 and a targeted Type 1 error rate of 5% a sample size of 50 was calculated we will plan to enroll 50 patients.

Ethics

No other IRB approval will be sought.

Informed consent will be obtained by one of the study investigators at the patient's preoperative visit in clinic or in the preoperative waiting area.

All data will be deidentified and assigned a random number. Data will be stored on a password protected file on a password protected computer.

Data handling and record keeping

All data will be deidentified and assigned a random number. Data will be stored on a password protected file on a password protected computer in the principal investigators office. All videos obtained will be de-identified and kept at the principal investigator's password protected computer in a locked office.

Quality control and assurance

Quality of video data and photographs will be assessed intraoperatively. A Storz representative will be available to aid with video equipment if technical difficulties were to occur.

There are no plans to have third party monitoring.

Publication Plan

We plan to submit the paper for publication to a high-quality ENT or Rhinology journal. Results will be available to the patients if requested.

References

1. Anderhuber, W., C. Walch, E. Nemeth, H. J. Semmelrock, A. Berghold, G. Ranftl, and H. Stammberger. "Plasma Adrenaline Concentrations during Functional Endoscopic Sinus Surgery." *The Laryngoscope* 109, no. 2 Pt 1 (February 1999): 204–7.

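### No test is assigned to the ordinal primary Boezaart grade: of the three generic rules, McNemar's test needs a cut-point the plan does not give and the rank-sum test ignores the pairing

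*Combined protocol and SAP*

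**What the plan says.** Study Design defines the primary comparison: "Our primary endpoint will be to compare surgical field visualization after the use of epinephrine or Oxymetazoline using the Boezaart grading scale". The operating surgeon grades the field at the end of the procedure, and a one-minute clip of each side is graded later: "These videos will be blindly reviewed and rated by all 3 surgeons using the Boezaart scale". The comparison is within patient: "The study will be a paired design study with one nasal cavity receiving epinephrine and the other receiving oxymetazoline".

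The Statistics section has three rules, each tied to a type of data and none to an endpoint:

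- Numerical measures are to be tested with a two-sided paired t-test.
- The rule for categories is: "Categorical data will be compared using the McNemar's test"
- The rule where normality fails is: "For non normally distributed data a Wilcoxon rank-sum test will be used"

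The threshold is given as "Statistical significance will be defined as less than 0.05". The documents do not list the Boezaart grades, say whether the grade counts as quantitative or categorical, or give a cut-point.

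**The concern.** An ordered grade with few levels can be placed under any of the three rules. It is a number, it is a category, and it will not be normally distributed. Two of these placements serve the trial badly. McNemar's test compares paired yes/no results, so the grades must first be collapsed at a threshold that would have to be chosen later, possibly with the data in view. The rank-sum test treats the two sides of one patient as independent samples and gives up the benefit of the paired design.

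What is at stake is the primary p-value. It would depend on an unstated choice between tests that differ widely in power, and under McNemar's test on a second free choice, the cut-point. The other two aims, blood loss and surgical time, are quantitative, so the categorical rule has no other stated endpoint to serve.

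**Working it through.** **The plan's own figure.** No power or sample size is given for the Boezaart grade. The 50 patients come from blood loss (SD 393 mL, difference 150 mL, power 0.8, 5% error). Taking 393 mL as the SD of the within-patient difference, n = (393 × (1.960 + 0.842) / 150)² = 53.9, so 54 (56 with the t distribution). This is near 50 but does not reproduce it. It does not bear on this point; only the 50 pairs are carried forward.

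**Inputs from the documents.** 50 pairs, two-sided tests, alpha 0.05.

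**Assumptions, because the documents are silent.** Six grades, 0 to 5. Each side's grade is a latent normal value (SD 1, centred on 2.5) rounded to a whole grade. Within-patient correlation is 0 to 0.7. The true difference between sides is 0.4 or 0.5 grade, split evenly around the centre. One grade per side is analysed. There were 6,000 simulated trials per row, so each power carries a simulation error of about ±0.013.

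**Power by test.** The central cut separates grades 0–2 from 3–5. The off-centre cut separates 0–3 from 4–5. McNemar results are asymptotic / exact.

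| Correlation | Shift | Signed-rank | Paired t | Rank-sum | McNemar, central | McNemar, off-centre |
|---|---|---|---|---|---|---|
| 0 | 0.4 | 0.474 | 0.479 | 0.468 | 0.361 / 0.275 | 0.246 / 0.179 |
| 0 | 0.5 | 0.646 | 0.656 | 0.644 | 0.512 / 0.413 | 0.360 / 0.270 |
| 0.3 | 0.4 | 0.591 | 0.600 | 0.465 | 0.434 / 0.339 | 0.276 / 0.198 |
| 0.3 | 0.5 | 0.781 | 0.786 | 0.667 | 0.597 / 0.497 | 0.406 / 0.317 |
| 0.5 | 0.4 | 0.721 | 0.727 | 0.462 | 0.491 / 0.400 | 0.307 / 0.223 |
| 0.5 | 0.5 | 0.890 | 0.895 | 0.691 | 0.664 / 0.586 | 0.437 / 0.338 |
| 0.7 | 0.4 | 0.878 | 0.879 | 0.432 | 0.568 / 0.476 | 0.367 / 0.255 |
| 0.7 | 0.5 | 0.978 | 0.979 | 0.728 | 0.779 / 0.703 | 0.530 / 0.405 |

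**Relative loss** = 1 − (power of the test / power of signed-rank). For correlation 0.5 and shift 0.4:

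- McNemar, central cut, asymptotic: 1 − 0.491/0.721 = 32%
- McNemar, central cut, exact: 1 − 0.400/0.721 = 45%
- Rank-sum: 1 − 0.462/0.721 = 36%

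Over the table:

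- McNemar, central cut: 20–35% (asymptotic), 28–46% (exact).
- McNemar, off-centre cut: 44–58% (asymptotic), 58–71% (exact).
- Rank-sum: about nil at correlation 0, 15–21% at 0.3, 22–36% at 0.5, 26–51% at 0.7.
- Paired t: no loss.

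**Sensitivity.** With latent SD 0.8 and the same shifts, the losses are smaller because the signed-rank test is often near full power: 8–22% (asymptotic) or 11–35% (exact) for McNemar at the central cut. If the shift is instead set so that the signed-rank test has about 80% power, with SD 0.8 or 1 and correlation 0 to 0.7, McNemar at the central cut loses 16–42% (asymptotic) or 28–54% (exact). In that setting rank-sum power falls from about 0.80 at correlation 0 to 0.30–0.37 at 0.7.

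**Behaviour with no true difference.** At SD 1, the rank-sum test rejects in 4.8% of trials at correlation 0, 0.9% at 0.5 and 0.2% at 0.7. Its fault is lost power, not false positives. McNemar's test with the most favourable of the five possible cuts picked after seeing the grades rejects, at correlation 0.5, in about 7% of trials (exact) or 14% (asymptotic).

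**The case against.** A reader might infer that the plan commits the sponsor to McNemar's test on the primary endpoint. It does not. The grade is described as "using the Boezaart grading scale, an inexpensive standardized rating scale used to analyze surgical field visualization during sinus surgery" and is never called categorical, and a numeric grade fits the paired t-test rule, which loses nothing. The elimination argument is also weaker than it looks. Lund-Mackay CT staging and the surgeon's mucosal grade are collected too, and although they are not named as endpoints, a generic paragraph may be meant to cover them. Even under the categorical rule, Bowker's symmetry test extends McNemar's to more than two categories.

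A reader might also infer that half the power is lost. That is one point in a range set by the assumed correlation, shift, cut-point and test version, none of which the documents give.

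Most of this stands, and it limits the claim to an unassigned test. It does not remove the defect. The plan names neither Bowker's test nor a paired rank test, so the only way to keep both the full scale and the pairing under its rules is to treat the grade as quantitative. A reader who regards it as ordered and non-normal is sent to McNemar's or the rank-sum test.

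**Conclusion.** Wrong as written. The plan does not say which of its rules governs the primary comparison, and two of the three do not suit paired ordered grades: one needs an unstated cut-point and the other discards the pairing. That the rank-sum test is unpaired in a paired design follows from the documents alone.

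The size rests on assumptions. With six grades, latent SD 1 and a shift of 0.4 to 0.5 grade, McNemar's test at its best cut gives up about a fifth to under a half of the signed-rank test's power, depending on version, and more at other cuts. The rank-sum penalty is nil without within-patient correlation and reaches about half at correlation 0.7 with the smaller shift. A narrower spread of grades shrinks these losses where power is near its ceiling.

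The documents do not support saying that a cut-point is forced or that a fixed share of power will be lost. Nor do they settle whether the live grade or the video grades are primary.

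**What to change.** In Statistics:

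1. State that the Boezaart comparison is a two-sided Wilcoxon signed-rank test on the within-patient difference, epinephrine side minus oxymetazoline side.
2. Replace rank-sum with signed-rank in the rule for non-normal data. This also corrects that rule for blood loss and surgical time.
3. Restrict McNemar's test to true yes/no outcomes, or delete it.

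Separately, the sponsor should name before any data are analysed which rating is primary: the surgeon's live grade, or a stated summary of the three video grades. That choice is the sponsor's, and the simulations above, which use one grade per side, do not decide it.

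The cost is a few sentences. Nothing changes for patients, data collection or sample size.

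### The fallback for non-normal data is an independent-samples test (Wilcoxon rank-sum) although every comparison in this trial is within-patient

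*Combined protocol and SAP*

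**What the plan says.** The Study Design section is explicit about the structure: "The study will be a paired design study with one nasal cavity receiving epinephrine and the other receiving oxymetazoline". Which side gets which drug is randomised within each patient. The inclusion criteria in that section ask for "patients undergoing bilateral endoscopic sinus surgery (ESS) in which the same sinuses and procedures on both sides are the same"; the restatement under Study Population leaves this condition out. The analysis set in the Statistics section is also paired: "All patients who are administered both randomized preoperative topical vasoconstrictors will be included in the study".

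The Statistics section then names three tests. Quantitative data get a two-sided paired t-test. For categories, "Categorical data will be compared using the McNemar's test". For the remaining case, "For non normally distributed data a Wilcoxon rank-sum test will be used". The signed-rank test is not mentioned anywhere, and no unpaired comparison is described. The plan gives no rule for judging normality and does not say whether raw values or paired differences are to be judged. It assigns no test to the Boezaart grade, which is the primary endpoint.

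**The concern.** The rank-sum test takes its null variance from two independent samples. Here the two samples are the left and right sides of the same 50 people. If the sides are positively correlated, the test overstates the variance of the comparison: p-values are too large and the gain from pairing is thrown away. If they are negatively correlated, p-values are too small. Only at zero correlation is the test correctly calibrated.

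Positive correlation is plausible, because both sides share the patient and the anaesthetic and the Study Design section requires the same sinuses and procedures on each side. The likely error is therefore a missed difference. For Aim 3 this has an awkward direction. The plan states "Hypothesis: There will be no difference in surgical time", so a real difference that the test failed to detect would look like confirmation of the plan's own hypothesis.

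The fallback could well be used. The planning figure is "The blood loss of 355 ± 393 mL seen in sevoflurane group from a previous study we performed". A standard deviation larger than the mean, for a quantity that should not be negative, suggests strong right skew. Surgical time per side and the Boezaart grade might also be sent to the fallback, though the plan does not say so.

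**Working it through.** **Inputs from the plan (Statistics section).** 50 patients, hence 50 pairs; significance level 0.05, two-sided; blood loss mean 355 mL, SD 393 mL; difference 150 mL; target power 0.8.

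**The plan's own figure.** The sample size does not reproduce exactly. With 393 mL taken as the SD of the paired difference, n = (393 × (1.960 + 0.842) / 150)² = 53.9, so 54 patients (56 with the t distribution), not 50. That is a separate matter. Only the 50 pairs are used below.

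**Assumptions, not in the documents.** Within-patient correlation ρ, varied from -0.3 to 0.7 on an underlying bivariate normal scale; the shapes of the distributions; the effect sizes for grade and time.

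**Step 1: type I error.** In large samples the variance of the rank-sum statistic under pairing is its independent-samples variance times (1 - r), where r = (6/π)·arcsin(ρ/2) is the rank correlation. The true level is then 2·[1 - Φ(1.96/√(1 - r))]. For example, ρ = 0.5 gives r = 0.483, 1.96/√0.517 = 2.72, and a level of 0.6%. Simulation used 20,000 trials per setting.

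| ρ | Formula, rank-sum | Simulated, rank-sum | Simulated, signed-rank |
|---|---|---|---|
| -0.3 | 8.4% | 8.2% | 4.7–5.1% |
| 0 | 5.0% | 4.9% | 4.7–5.1% |
| 0.3 | 2.0% | 2.0–2.2% | 4.7–5.1% |
| 0.5 | 0.6% | 0.7% | 4.7–5.1% |
| 0.7 | 0.05% | 0.1% | 4.7–5.1% |

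**Step 2: power for blood loss.** A lognormal with mean 355 and SD 393 has log-SD √ln(1 + (393/355)²) = 0.894. The plan's difference is "With a proposed difference of 150ml of blood loss with a targeted power of 0.8", modelled as one side multiplied by 205/355. If 355 ± 393 mL is instead a whole-patient figure, the side mean is 177.5 mL, the side SD is set so that the two sides sum to an SD of 393 mL, and the effect is 75 mL per side (multiplier 102.5/177.5). Each power setting used 10,000 trials. Entries are rank-sum vs signed-rank, in %.

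| Setting | ρ = 0 | 0.3 | 0.5 | 0.7 |
|---|---|---|---|---|
| 150 mL, figure read per side | 84 vs 80 | 88 vs 91 | 92 vs 97 | 95 vs 99.9 |
| 75 mL per side, figure read as whole patient | 66 vs 60 | 74 vs 79 | 82 vs 92 | 92 vs 99 |

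**Step 3: power for a graded endpoint.** Six levels with assumed probabilities 1, 2, 3, 3, 2, 1 twelfths, and a shift on the latent scale.

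| Setting | ρ = 0 | 0.3 | 0.5 | 0.7 |
|---|---|---|---|---|
| 0.4 SD shift | 47 vs 47 | 47 vs 60 | 47 vs 73 | 47 vs 91 |
| 0.7 SD shift | 91 vs 91 | 94 vs 97 | 97 vs 99 | 99 vs 100 |

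**Step 4: surgical time (Aim 3).** Lognormal times with a true 15% difference (assumed). Entries are the chance of a non-significant result, rank-sum vs signed-rank, in %, given that the fallback is used.

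| Setting | ρ = 0 | 0.3 | 0.5 | 0.7 |
|---|---|---|---|---|
| CV 0.5 | 62 vs 63 | 64 vs 52 | 66 vs 39 | 69 vs 17 |
| CV 0.3 | 24 vs 25 | 20 vs 13 | 16 vs 4 | 11 vs 0.2 |

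**Step 5: how often the fallback would be used.** Suppose normality is judged by a Shapiro-Wilk test at 5% on the paired differences (an assumption), over correlations 0 to 0.7. The blood-loss model then triggers the fallback in about 90–97% of trials. The surgical-time model triggers it in about 34–52% at CV 0.5 and 13–21% at CV 0.3; the paired t-test is used otherwise. Over all such trials at CV 0.5 and ρ = 0.7, non-significance is about 44% with rank-sum as the fallback and 18% with signed-rank.

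**The case against.** The strongest reply is that this is one wrong word. The paired t-test and McNemar's test sit beside it, the analysis set requires both drugs, and an analyst who understood the design might well run signed-rank anyway. That is probably how the error arose. It does not remove it: following the text literally gives the wrong test, and silently using signed-rank departs from the written plan.

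The second reply concerns size, and much of it stands. At the only effect the plan states, 150 mL read per side, rank-sum power stays above 0.8 at every correlation from 0 to 0.7, and at zero correlation it is slightly higher than signed-rank. The large losses depend on correlations, effect sizes, grade levels and coefficients of variation that the plan does not supply, so they show sensitivity and not expected harm. Inflated type I error needs negative correlation, for which there is no particular reason here.

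Three narrower points also stand:
- The Aim 3 figures in step 4 apply only when the fallback is triggered; step 5 shows the smaller overall effect.
- A planning SD above the mean describes one marginal distribution and suggests, but does not prove, that the paired differences are non-normal.
- Reading non-significance as support for no difference in surgical time is a flaw of its own, which signed-rank would not cure.

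**Conclusion.** The concern holds. The plan names an independent-samples test for paired data, and nothing in the document corrects it. With 50 pairs, the true level of a nominal 5% test runs from about 8% at a correlation of -0.3 to about 0.1% at 0.7, and is right only at zero. Under the more plausible positive correlation the test is conservative, so no false claim of benefit follows, but real differences can be missed. The cost is at most about 5 power points at the plan's 150 mL. It reaches 26 points (47 vs 73%) for an assumed 0.4 SD shift in grade at a correlation of 0.5. These sizes rest on the assumed correlations, distributions and effects, and apply only where the fallback is used. The mismatch between test and design rests on none of them. It should be fixed, but it does not undermine the trial.

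**What to change.** In the Statistics section, replace the rank-sum test with the Wilcoxon signed-rank test applied to the within-patient difference (epinephrine side minus oxymetazoline side). As a secondary improvement, name it as the test for the ordinal Boezaart grade and keep McNemar's test for two-level outcomes. For the grade, the plan would also need to say how the operating surgeon's rating and the three video ratings become one value per side.

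The change of test is one or two sentences. It needs no additional data and no additional patients.

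### The 50 patients stated for 80% power do not follow from the plan's own inputs, and the SD used is not shown to be the SD of the within-patient side difference

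*Combined protocol and SAP*

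**What the plan says.** All of the sample-size reasoning is in the second paragraph of the Statistics section of the combined protocol and SAP. The variability comes from the authors' own earlier work: "The blood loss of 355 ± 393 mL seen in sevoflurane group from a previous study we performed", in which oxymetazoline was used. The target is "With a proposed difference of 150ml of blood loss with a targeted power of 0.8 and a targeted Type 1 error rate of 5" percent, and the result is 50 patients. The first paragraph of the same section fixes the test: "For quantitative data a 2-tailed paired t-test will be used".

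The Study Design section gives the structure: "The study will be a paired design study with one nasal cavity receiving epinephrine and the other receiving oxymetazoline". It also ranks the endpoints. On the primary: "Our primary endpoint will be to compare surgical field visualization after the use of epinephrine or Oxymetazoline using the Boezaart grading scale". On the secondary: "Our secondary endpoint will be to compare the amount of blood loss use after the use of epinephrine or Oxymetazoline".

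The document gives no sample-size formula, SD of the side-to-side difference, within-patient correlation or dropout allowance. It does not say whether 355 ± 393 mL refers to one side or to the whole operation.

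**The concern.** A paired t-test compares the mean within-patient difference with the SD of that difference. The only SD in the plan is the spread of blood loss across patients in one group of another study. The two can differ widely in either direction, depending on how strongly the two sides of one patient agree and on whether the quoted figure covers one side or both. The first question is whether the number reproduces if 393 mL is simply used as given. The second is whether using it that way is justified.

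The reading of a null result is at stake. A non-significant blood-loss comparison could be reported as coming from a test with 80% power for 150 mL, which the document does not establish. The calculation also concerns only the secondary endpoint, so a reader has no statement of what 50 patients can detect on the primary one.

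**Working it through.** **Inputs (Statistics section):** difference 150 mL; SD 393 mL; two-sided 5%; power 0.80; paired t-test; stated n = 50.

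**Step 1: try to reproduce 50, taking 393 mL as the SD of the paired difference.**

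- Standardised difference: 150/393 = 0.382.
- Normal approximation: n = (1.960 + 0.842)² × (393/150)² = 53.9, so 54.
- Noncentral t: 55.8, so 56 (power 0.801 at 56, 0.794 at 55).
- Power at n = 50, normal: 150/(393/√50) = 2.699, and Φ(2.699 − 1.960) = 0.770.
- Power at n = 50, noncentral t: 0.754.

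**Step 2: try other routes to 50.**

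| Variant | Patients needed |
|---|---|
| One-sided paired | 43 (normal), 44 (t) |
| Two independent groups, two-sided | 108 (normal), 109 (t) per group |
| Two-sided paired, Wilcoxon efficiency 0.955 | 57 to 59 |
| Two-sided paired, 5% to 20% dropout | 57 to 70 |
| One-sided paired, 10% dropout | 48 to 49 |
| One-sided paired, 15% dropout | 51 to 52 |
| One-sided paired, efficiency 0.864 | 50 to 51 |

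Only a one-sided test with an added, unstated factor comes near 50, and the plan specifies a two-tailed test.

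**Step 3: find what would make 80% true at n = 50.** The paired t-test then detects 0.404 SD of the difference.

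- Largest SD of the difference for 150 mL: 150/0.404 = 371 mL (about 379 mL by normal approximation).
- If that SD is 393 mL, the detectable difference is 0.404 × 393 = 159 mL.

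**Step 4: vary the meaning of 393 mL.** Both readings are assumptions, as are the correlations ρ between a patient's two sides. Equal side variances are assumed in both.

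*393 mL is the SD of the two-side total.* Then SD of the difference = 393 × √((1 − ρ)/(1 + ρ)).

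| ρ | SD of difference (mL) | Power for 150 mL, n = 50 | n for 80% |
|---|---|---|---|
| 0 | 393 | 75.4% | 56 |
| 0.06 | 370 | 80.2% | 50 |
| 0.3 | 288 | 95.0% | 31 |

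Power reaches 80% at ρ ≈ 0.057. With an even split, one side's mean loss would be 355/2 = 177.5 mL, so 150 mL would be 150/177.5 = 85% of it.

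*393 mL is a per-side SD.* Then SD of the difference = 393 × √(2(1 − ρ)).

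| ρ | SD of difference (mL) | Power for 150 mL, n = 50 | n for 80% | Detectable with 50 (mL) |
|---|---|---|---|---|
| 0 | 556 | 46.5% | 110 | 225 |
| 0.3 | 465 | 60.9% | 78 | 188 |
| 0.5 | 393 | 75.4% | 56 | 159 |
| 0.6 | 352 | 84.1% | 46 | 142 |
| 0.7 | 304 | 92.7% | 35 | 123 |

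Power reaches 80% at ρ ≈ 0.55. Using 393 mL directly as the SD of the difference therefore amounts to assuming ρ = 0.5 on this reading, or ρ = 0 on the two-side-total reading.

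**The case against.** The strongest reply is that the key input is missing rather than miscalculated. With an unstated correlation of about 0.55 (per-side SD) or 0.06 (two-side total), 50 patients for 80% would be right, so the fair charge would be that the figure cannot be verified. Even on the direct reading the gap is only 3 to 5 power points. Further, the source groups were defined by anaesthetic, which is given to the whole patient, so 355 ± 393 mL is more naturally a whole-patient loss. On that reading power is at least 75% at any non-negative correlation, and the 46.5% and 61% figures do not arise. The Study Design section also calls the trial a pilot, for which formal power on the primary endpoint is less clearly required. Finally, an SD larger than the mean suggests skewed data, so a paired t-test may not be the analysis that is run.

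Much of this is fair. The direct-reading gap is modest, the whole-patient reading is plausible, and every figure here is a paired-t benchmark. It is also true that the planned test can address only a difference between sides, so 150 mL most naturally means that; the plan should still say so, because its reference figure may be on a different scale.

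The reply does not restore the 80%. The plan states neither correlation and does not say which unit applies, and no calculation confined to its stated inputs and test gives 50. A pilot may be small, but this one chose to make a formal power claim, which should follow from what is written.

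**Conclusion.** The concern holds. On the direct reading the error is small: 56 patients needed against 50 stated, or 75% power against 80%. The missing SD of the side difference matters more, because over the range of assumptions examined power at 50 patients lies anywhere from 46.5% to 95%. The document gives nothing that narrows this.

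These figures assume a two-sided 5% paired t-test with approximately normal differences and no dropout, and the correlation tables also assume equal side variances. They do not show that the trial is underpowered; true power could be below or above 80%.

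The absence of any power statement for the Boezaart endpoint is a secondary point, softened by the pilot label, but it belongs in the same correction.

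**What to change.** Keep 50 patients and rewrite the sample-size paragraph.

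1. State whether 355 ± 393 mL and 150 mL are per side or per patient.
2. State the assumed SD of the within-patient side difference, or the correlation from which it is derived.
3. Replace the 80% claim with the power that follows, and add a short table over plausible correlations, labelled as paired-t approximations. Write 75% for 150 mL, or 80% for 159 mL, only if the SD of the difference is explicitly assumed to be 393 mL. Keep 80% for 150 mL only if an SD of 371 mL or less is justified.
4. Say that the calculation supports the secondary endpoint and that the primary Boezaart endpoint was not formally powered. A detectable effect of 0.40 SD of the paired difference may be given as a rough benchmark only, because the scale is an ordinal grade and the plan does not fix its test.

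The cost is one paragraph and a small table, with no extra patients. The downside is a less favourable stated power, unless the smaller SD can be justified, and an open statement that the primary endpoint was not formally powered.
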